##### **8.5.2. Secondary Analyses**

The approach used for primary efficacy analysis will be applied for secondary efficacy endpoint as in Section 8.5.1.

#### **8.6. Safety Analysis**

All safety data collected on or after the date that IMP was first dispensed up to the date of last dose of IMP will be summarized by treatment group (according to the IMP received). Data for the pretreatment and TFFU periods will be included in data listings.

##### **8.6.1. Primary Safety Analysis**

The change from baseline in  $eGFR_{CKD-EPI}$  at Week 24 will be summarized.

##### **8.6.2. Secondary Safety Analyses**

The change from baseline in  $eGFR_{CKD-EPI}$  at Week 48 will be performed.

The percent change from baseline in hip and spine BMD at Weeks 24 and 48 will be summarized.

The change from baseline in serum creatinine at Weeks 24 and 48 will be summarized.

### **8.6.3. Extent of Exposure**

A subject's extent of exposure to IMP data will be generated from the IMP administration data. Exposure data will be summarized by treatment group.

### **8.6.4. Adverse Events**

Clinical and laboratory adverse events will be coded using the Medical Dictionary for Regulatory Activities (MedDRA). System Organ Class (SOC), High-Level Group Term (HLGT), High-Level Term (HLT), Preferred Term (PT), and Lower-Level Term (LLT) will be attached to the clinical database.

Events will be summarized on the basis of the date of onset for the event. A treatment-emergent adverse event will be defined as any adverse event that begins on or after the date of first dose of treatment up to the date of last dose of treatment. Continuing adverse events diagnosed prior to the start of treatment and worsening in severity grade, or non-serious adverse events at baseline which become serious, or adverse events resulting in treatment discontinuation after the start of treatment will also be considered treatment-emergent.

Summaries (number and percentage of subjects) of treatment-emergent adverse events (by SOC, and PT) will be provided by treatment group.

### **8.6.5. Laboratory Evaluations**

Selected laboratory data (using units) will be summarized using only observed data. Data and change from baseline at all scheduled time points will be summarized.

Graded laboratory abnormalities will be defined using the grading scheme in [Appendix 5](#).

Incidence of treatment-emergent laboratory abnormalities, defined as values that increase at least one toxicity grade from baseline at any time post baseline up to and including the date of last dose of treatment will be summarized by treatment group. If baseline data are missing, then any graded abnormality (i.e., at least a Grade 1) will be considered treatment emergent.

Laboratory abnormalities that occur before the first dose of treatment or after the subject has been discontinued from treatment will be included in a data listing.

### **8.7. Pharmacokinetic Analysis**

Pharmacokinetic parameters will be listed and summarized for TAF and TFV using descriptive statistics (eg, sample size, arithmetic mean, geometric mean, % coefficient of variation, standard deviation, median, minimum, and maximum). Plasma concentrations of TAF and TFV over time will be plotted in semi logarithmic and linear formats as mean  $\pm$  standard deviation.

CCI

## **8.8. Biomarker Analysis**

Selected bone biomarkers, including C-type collagen sequence (CTX) and procollagen type 1 N-terminal propeptide (P1NP), and selected renal biomarkers, including urine retinol binding protein, and urine beta-2-microglobulin, will be summarized by treatment group and visit using descriptive statistics.

## **8.9. Sample Size**

This is an exploratory study. No formal sample size calculation was performed.

## **8.10. Data Monitoring Committee**

A data monitoring committee (DMC) will review the progress of the study and perform review of safety data once after 30 subjects have completed 12 weeks of treatment, and provide recommendation to Gilead whether the nature, frequency, and severity of adverse effects associated with study treatment warrant the early termination of the study in the best interests of the participants, whether the study should continue as planned, or the study should continue with modifications. The DMC may also provide recommendations as needed regarding study design. Subsequent meetings will be held on an ad hoc basis.

The DMC's specific activities will be defined by a mutually agreed charter, which will define the DMC's membership, conduct and meeting schedule.

While the DMC will be asked to advise Gilead regarding future conduct of the study, including possible early study termination, Gilead retains final decision-making authority on all aspects of the study.

## **9. RESPONSIBILITIES**

### **9.1. Investigator Responsibilities**

#### **9.1.1. Good Clinical Practice**

The investigator will ensure that this study is conducted in accordance with the principles of the Declaration of Helsinki (as amended in Edinburgh, Tokyo, Venice, Hong Kong, and South Africa), International Conference on Harmonisation (ICH) guidelines, or with the laws and regulations of the country in which the research is conducted, whichever affords the greater protection to the study subject. The investigator will ensure adherence to the basic principles of Good Clinical Practice, as outlined in 21 CFR 312, subpart D, “Responsibilities of Sponsors and Investigators,” 21 CFR, part 50, 1998, and 21 CFR, part 56, 1998.

The investigator and all applicable subinvestigators will comply with 21 CFR, Part 54, 1998, providing documentation of their financial interest or arrangements with Gilead, or proprietary interests in the investigational drug under study. This documentation must be provided prior to the investigator’s (and any subinvestigator’s) participation in the study. The investigator and subinvestigator agree to notify Gilead of any change in reportable interests during the study and for 1 year following completion of the study. Study completion is defined as the date when the last subject completes the protocol-defined activities.

#### **9.1.2. Institutional Review Board (IRB)/Independent Ethics Committee (IEC) Review and Approval**

The investigator (or sponsor as appropriate according to local regulations) will submit this protocol, informed consent form, and any accompanying material to be provided to the subject (such as advertisements, subject information sheets, or descriptions of the study used to obtain informed consent) to an IRB/IEC. The investigator will not begin any study subject activities until approval from the IRB/IEC has been documented and provided as a letter to the investigator.

Before implementation, the investigator will submit to and receive documented approval from the IRB/IEC any modifications made to the protocol or any accompanying material to be provided to the subject after initial IRB/IEC approval, with the exception of those necessary to reduce immediate risk to study subjects.

#### **9.1.3. Informed Consent**

The investigator is responsible for obtaining written informed consent from each individual participating in this study after adequate explanation of the aims, methods, objectives, and potential hazards of the study and before undertaking any study-related procedures. The investigator must use the most current IRB/IEC approved consent form for documenting written informed consent. Each informed consent (or assent as applicable) will be appropriately signed and dated by the subject or the subject’s legally authorized representative and the person

conducting the consent discussion, and also by an impartial witness if required by IEC or local requirements. CCI

#### **9.1.4. Confidentiality**

The investigator must assure that subjects' anonymity will be strictly maintained and that their identities are protected from unauthorized parties. Only subject initials, date of birth, another unique identifier (as allowed by local law) and an identification code will be recorded on any form or biological sample submitted to the Sponsor, the IRB/IEC or laboratory. Laboratory specimens must be labeled in such a way as to protect subject identity while allowing the results to be recorded to the proper subject. Refer to specific laboratory instructions in the lab manual. NOTE: The investigator must keep a screening log showing codes, names, and addresses for all subjects screened and for all subjects enrolled in the trial. Subject data will be processed in accordance with all applicable regulations.

The investigator agrees that all information received from Gilead, including but not limited to the investigator brochure, this protocol, CRF/eCRF, the IMP, and any other study information, remain the sole and exclusive property of Gilead during the conduct of the study and thereafter. This information is not to be disclosed to any third party (except employees or agents directly involved in the conduct of the study or as required by law) without prior written consent from Gilead. The investigator further agrees to take all reasonable precautions to prevent the disclosure by any employee or agent of the study site to any third party or otherwise into the public domain.

#### **9.1.5. Study Files and Retention of Records**

The investigator must maintain adequate and accurate records to enable the conduct of the study to be fully documented and the study data to be subsequently verified. These documents should be classified into at least the following two categories: (1) investigator's study file, and (2) subject clinical source documents.

The investigator's study file will contain the protocol/amendments, CRF and query forms, IEC and governmental approval with correspondence, informed consent, drug records, staff curriculum vitae and authorization forms, and other appropriate documents and correspondence.

The required source data should include sequential notes containing at least the following information for each subject:

- Subject identification (name, date of birth, gender);
- Documentation that subject meets eligibility criteria, i.e., history, physical examination, and confirmation of diagnosis (to support inclusion and exclusion criteria);
- Documentation of the reason(s) a consented subject is not enrolled

- Participation in study (including study number);
- Study discussed and date of informed consent;
- Dates of all visits;
- Documentation that protocol specific procedures were performed;
- Results of efficacy parameters, as required by the protocol;
- Start and end date (including dose regimen) of IMP, including dates of dispensing and return;
- Record of all adverse events and other safety parameters (start and end date, and including causality and severity);
- Concomitant medication (including start and end date, dose if relevant; dose changes);
- Date of study completion and reason for early discontinuation, if it occurs.

All clinical study documents must be retained by the investigator until at least 2 years or according to local laws, whichever is longer, after the last approval of a marketing application in an ICH region (ie, United States, Europe, or Japan) and until there are no pending or planned marketing applications in an ICH region; or, if no application is filed or if the application is not approved for such indication, until 2 years after the investigation is discontinued and regulatory authorities have been notified. Investigators may be required to retain documents longer if specified by regulatory requirements, by local regulations, or by an agreement with Gilead. The investigator must notify Gilead before destroying any clinical study records.

Should the investigator wish to assign the study records to another party or move them to another location, Gilead must be notified in advance.

If the investigator cannot provide for this archiving requirement at the study site for any or all of the documents, special arrangements must be made between the investigator and Gilead to store these records securely away from the site so that they can be returned sealed to the investigator in case of an inspection. When source documents are required for the continued care of the subject, appropriate copies should be made for storage away from the site.

#### **9.1.6. Case Report Forms**

For each subject consented, an eCRF will be completed by an authorized study staff member whose training for this function is documented according to study procedures. eCRF should be completed on the day of the subject visit to enable the sponsor to perform central monitoring of safety data. The Eligibility Criteria eCRF should be completed only after all data related to eligibility have been received. Subsequent to data entry, a study monitor will perform source data verification within the EDC system. Original entries as well as any changes to data fields will be stored in the audit trail of the system. Prior to database lock (or any interim time points as described in the clinical data management plan), the investigator will use his/her log in credentials to confirm that the forms have been reviewed, and that the entries accurately reflect

the information in the source documents. The eCRF capture the data required per the protocol schedule of events and procedures. System-generated or manual queries will be issued to the investigative site staff as data discrepancies are identified by the monitor or internal Gilead staff, who routinely review the data for completeness, correctness, and consistency. The site coordinator is responsible for responding to the queries in a timely manner, within the system, either by confirming the data as correct or updating the original entry, and providing the reason for the update (e.g., data entry error). At the conclusion of the trial, Gilead will provide the site with a read-only archive copy of the data entered by that site. This archive must be stored in accordance with the records retention requirements outlined in Section 9.1.5.

#### **9.1.7. Investigational Medicinal Product Accountability and Return**

Gilead recommends that used and unused IMP supplies be returned to the shipping facility from which it came for eventual destruction. The study monitor will provide instructions for return. If return is not possible, the study monitor will evaluate each study center's IMP disposal procedures and provide appropriate instruction for destruction of unused IMP supplies. If the site has an appropriate standard operating procedure (SOP) for drug destruction as determined by Gilead, the site may destroy used (empty or partially empty) and unused IMP supplies in accordance with that site's approved SOP. A copy of the site's approved SOP will be obtained for central files.

If IMP is destroyed on site, the investigator must maintain accurate records for all IMP destroyed. Records must show the identification and quantity of each unit destroyed, the method of destruction, and the person who disposed of the IMP. Upon study completion, copies of the IMP accountability records must be filed at the site. Another copy will be returned to Gilead.

The study monitor will review IMP supplies and associated records at periodic intervals.

#### **9.1.8. Inspections**

The investigator will make available all source documents and other records for this trial to Gilead's appointed study monitors, to IRB/IEC, or to regulatory authority or health authority inspectors.

#### **9.1.9. Protocol Compliance**

The investigator is responsible for ensuring the study is conducted in accordance with the procedures and evaluations described in this protocol.

### **9.2. Sponsor Responsibilities**

#### **9.2.1. Protocol Modifications**

Protocol modifications, except those intended to reduce immediate risk to study subjects, may be made only by Gilead. The investigator must submit all protocol modifications to the IEC in accordance with local requirements and receive documented IEC approval before modifications can be implemented.

## **9.2.2. Study Report and Publications**

A clinical study report (CSR) will be prepared and provided to the regulatory agency. Gilead will ensure that the report meets the standards set out in the ICH Guideline for Structure and Content of Clinical Study Reports (ICH E3). Note that an abbreviated report may be prepared in certain cases.

Investigators in this study may communicate, orally present, or publish in scientific journals or other scholarly media only after the following conditions have been met:

the results of the study in their entirety have been publicly disclosed by or with the consent of Gilead in an abstract, manuscript, or presentation form or the study has been completed at all study sites for at least 2 years.

The investigator will submit to Gilead any proposed publication or presentation along with the respective scientific journal or presentation forum at least 30 days before submission of the publication or presentation.

No such communication, presentation, or publication will include Gilead's confidential information (see Section 9.1.4).

The investigator will comply with Gilead's request to delete references to its confidential information (other than the study results) in any paper or presentation and agrees to withhold publication or presentation for an additional 60 days in order to obtain patent protection if deemed necessary.

## **9.3. Joint Investigator/Sponsor Responsibilities**

### **9.3.1. Payment Reporting**

Investigators and their study staff may be asked to provide services performed under this protocol, e.g., attendance at Investigator's Meetings. If required under the applicable statutory and regulatory requirements, Gilead will capture and disclose to Federal and State agencies any expenses paid or reimbursed for such services, including any clinical trial payments, meal, travel expenses or reimbursements, consulting fees, and any other transfer of value.

### **9.3.2. Access to Information for Monitoring**

In accordance with regulations and guidelines, the study monitor must have direct access to the investigator's source documentation in order to verify the accuracy of the data recorded in the CRF/eCRF.

The monitor is responsible for routine review of the CRF/eCRF at regular intervals throughout the study to verify adherence to the protocol and the completeness, consistency, and accuracy of the data being entered on them. The monitor should have access to any subject records needed to verify the entries on the CRF/eCRF. The investigator agrees to cooperate with the monitor to ensure that any problems detected through any type of monitoring (central, on site) are resolved.

### **9.3.3. Access to Information for Auditing or Inspections**

Representatives of regulatory authorities or of Gilead may conduct inspections or audits of the clinical study. If the investigator is notified of an inspection by a regulatory authority the investigator agrees to notify the Gilead medical monitor immediately. The investigator agrees to provide to representatives of a regulatory agency or Gilead access to records, facilities, and personnel for the effective conduct of any inspection or audit.

### **9.3.4. Study Discontinuation**

Both the sponsor and the investigator reserve the right to terminate the study at any time. Should this be necessary, both parties will arrange discontinuation procedures and notify the appropriate regulatory authority(ies), IRBs, and IECs. In terminating the study, Gilead and the investigator will assure that adequate consideration is given to the protection of the subjects' interests.

## 11. APPENDICES

- Appendix 1. Investigator Signature Page
- Appendix 2. Study Procedures Table
- Appendix 3. **CCI**
- Appendix 4. Management of Clinical and Laboratory Adverse Events
- Appendix 5. GSI Grading Scale for Severity of Adverse Events and Laboratory Abnormalities
- Appendix 6. Pregnancy Precautions, Definition for Female of Childbearing Potential, and Contraceptive Requirements

**Appendix 2. Study Procedures Table**

	Screening (-45 Days)	BL	4	4 + 24 Hrs	8	8 + 24 Hrs	12	20	24	36	48	ED	TFFU a
	Visit Windows a	± 3 Days											± 7 Days
Written Informed Consent	X												
Review of Inclusion/Exclusion Criteria	X	X											
Medical History, including HBV history	X	X											
Review Concomitant Medications	X	X	X		X		X	X	X	X	X	X	X
Adverse Events	X	X	X	X	X	X	X	X	X	X	X	X	X
Complete Physical Examination including vital signs, and weight	X	X					X		X		X	X	
Height	X												
Symptom-directed Physical Exam			X		X			X		X			X
Body weight	X	X	X		X		X	X	X	X	X	X	X
Vital Signs b	X	X	X		X		X	X	X	X	X	X	X
Randomization		X											
DXA c (spine & hip)	X								X		X	X	
FRAX ® Fracture Risk Assessment Tool		X											

[figure not shown]

	Screening (-45 Days)	BL	4	4 + 24 Hrs	8	8 + 24 Hrs	12	20	24	36	48	ED	TFFU g
	Visit Windows a	± 3 Days											± 7 Days
Cr EDTA renal scan		X									X		
Study Drug Accountability			X		X		X	X	X	X	X	X	
Study Drug Dispensed/Retrieved		X	X		X		X	X	X	X	X	X	
Dosing in-clinic d			X		X								
Serum Chemistry and Liver Function Tests e	X	X	X		X		X	X	X	X	X	X	X
eGFR CKD-EPI	X	X	X		X		X	X	X	X	X	X	X
Hematology	X	X	X		X		X	X	X	X	X	X	X
Cystatin C (for estimated GFR)	X	X	X				X		X		X	X	X
Plasma HBV DNA Levels	X	X	X		X		X	X	X	X	X	X	X
Serum HBsAg (qualitative) f	X	X							X		X	X	X
Serum HBeAg (qualitative) f	X	X							X		X	X	X
Sample collection for HBV Resistance Surveillance g		X	X		X		X	X	X	X	X	X	X
HIV-1, HDV, HCV	X												
α-fetoprotein	X								X		X	X	X
Fibrotest ®		X							X		X	X	X
Vitamin D		X							X		X	X	X

	Screening (-45 Days)	BL	4	4 + 24 Hrs	8	8 + 24 Hrs	12	20	24	36	48	ED	TFFU q
	Visit Windows a	± 3 Days											± 7 Days
Whole blood for PBMC		X							X		X		
Plasma PK m		X	X		X		X	X	X	X	X		
Fasting Blood for Bone Biomarkers h		X	X				X		X		X	X	
Fasting Blood for Renal Biomarkers h		X	X				X		X		X	X	
Fasting Urine for Renal Biomarkers i		X	X				X		X		X	X	
Fasting Metabolic Panel o		X							X		X	X	
Serum Pregnancy Test l	X												
Urine Pregnancy Test l		X	X		X		X	X	X	X	X	X	X
Urinalysis	X	X	X				X		X		X	X	X
Urine drug screen	X												
CCI													
Health Related Quality of Life Surveys l		X							X		X	X	

	Screening (-45 Days)	BL	4	4 + 24 Hrs	8	8 + 24 Hrs	12	20	24	36	48	CCCI	TFFU a
	Visit Windows a		± 3 Days										± 7 Days
Imaging Test a	X												

[figure not shown]
- a The out of visit window is ± 3 days until Week 48, CCI, and ± 7 days for TFFU visits.
- b Vital signs include blood pressure, pulse, respiration rate, and temperature.
- c The initial DXA will be performed during Screening and should be completed at least 14 days prior to the first dose of study drug. The Week 48 DXA window is – 3 days only. DXA is required for Early Discontinuation (ED) visit if not done within the last 24 weeks.
- d It is preferred that subjects take their study drug according to a morning dosing schedule; subjects who elect to dose in the evening the previous day are not required to have in-clinic dosing and provide the single PK sample being collected at Week 4 and 8 visits.
- e Serum chemistry and Liver Function Tests: alkaline phosphatase, AST, ALT, GGT, total bilirubin, direct and indirect bilirubin, total protein, albumin, LDH, CPK, bicarbonate, BUN, calcium, chloride, creatinine, glucose, phosphorus, magnesium, potassium, sodium, uric acid, and amylase (reflex lipase testing is performed in subjects with total amylase > 1.5 × ULN). At Baseline, Weeks 24, 48, 96, 144 and 192/ED, subject will be fasting for serum glucose and metabolic panel. Coagulation panel will be done at Screening and then as a reflex only test for ALT flares.
- f Qualitative HBsAg and HBeAg will be performed at Screening, Baseline (BL), Weeks 24, 48, 72, 96, 120, 144, 168, 192 and ED. HBeAb and HBsAb testing will be performed as reflex testing as needed.
- g Sequence analysis of the HBV pol/RT for possible resistance mutation(s) may be attempted for any subject that experiences viremia (HBV DNA > 69 IU/mL).
- h Blood for selected bone biomarkers and renal biomarkers will be collected in a fasted state. Required for ED visit if the last sample was collected > 24 weeks prior.
- i Urine for selected renal biomarkers will be collected in a fasted state. Required for ED visit if the last sample was collected > 24 weeks prior.
- j For female subjects of childbearing potential, the serum beta-HCG test will be performed at Screening. Urine test will be performed at all other visits as indicated. Positive urine test will be confirmed with serum test. Pregnancy tests should include prevention counseling.
- k [Redacted]
- l Health Related Quality of Life surveys included in this study are: SF-36, CLDQ, and WPAI. The surveys will be administered at BL, Weeks 24, 48, 96, 144, 192 and Early Discontinuation Visits, if applicable.
- m At Weeks 8 and 24 the plasma PK samples should be collected between 15 minutes and 4 hours post-dose.
- n At Screening, α-fetoprotein (AFP) will be measured and subjects with an AFP >50 ng/mL or other findings concerning HCC must undergo imaging test (e.g., CT scan) to rule out HCC.
- o Fasting glucose and lipid panel (total cholesterol, HDL, direct LDL, triglycerides)
- p At Week 48, per Principal Investigator (PI) discretion, subjects will be eligible to receive TAF 25 mg daily CCI [Redacted]
- q Subjects who have received at least one dose of TAF and discontinue treatment prematurely CCI [Redacted] will be followed every 4 weeks for 24 weeks off treatment in accordance with TFFU visits or until initiation of alternative CHB therapy, whichever comes first.

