**Criteria for Evaluation:**

Safety:

Adverse events (AEs) and clinical laboratory tests will be collected at every visit throughout the study, CCI [REDACTED]. The proportion of subjects in each treatment arm with an AE leading to early discontinuation of study drug(s) and proportion of subjects with serious adverse events will be summarized through Weeks 24, 48, CCI [REDACTED].

The **primary safety endpoint** is:

- Change from baseline in eGFRCKD-EPI of TAF 25 mg QD versus TDF-containing regimens at Week 24

The **secondary safety endpoints** are:

- Percent change from baseline in hip and spine bone mineral density (BMD) of TAF 25 mg QD versus TDF-containing regimens at Weeks 24 and 48
- Change from baseline in serum creatinine of TAF 25 mg QD versus TDF-containing regimens at Weeks 24 and 48
- Change from baseline in eGFRCKD-EPI of TAF 25 mg QD versus TDF-containing regimens at Week 48

Efficacy:

The **primary efficacy endpoint** is:

- Proportion of subjects with HBV DNA < 20 IU/mL at Week 24

The **secondary efficacy endpoint** is:

- Proportion of subjects with HBV DNA < 20 IU/mL at Week 48

Exploratory endpoints:

█ [REDACTED]

█ [REDACTED]

█ [REDACTED]

█ [REDACTED]

█ [REDACTED]

█ [REDACTED]

█ [REDACTED]

█ [REDACTED]

█ [REDACTED]

█ [REDACTED]

Pharmacokinetics:

All subjects will have single plasma PK samples drawn at each treatment visit through Week 48. At Weeks 8 and 24 the PK sample should be collected between 15 minutes and 4 hours post-dose.

CCI [REDACTED]

[REDACTED]

---

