### 6.3. Treatment Assessments

#### 6.3.1. Study Week Assessments (Weeks 4-48)

The following evaluations will be performed at Weeks 4-48 unless specified;

- Provide Health Related Quality of Life surveys (HRQoL): SF-36, CLDQ, WPAI to be completed by subjects at visit (**Weeks 24, and 48 only**)
- Perform complete physical examination including, vital signs (blood pressure, pulse, respiration rate and temperature), and body weight (**Weeks 12, 24, and 48 only**)
- Perform symptom-driven physical examination including vital signs, and body weight (**Weeks 4, 8, 20, and 36 only**)
- Review of AEs and concomitant medications
- Cr EDTA Renal Scan (**Week 48 only**)
- Perform DXA scan of spine and hip (**Weeks 24 and 48 only**)
- Perform study drug accountability
- Dispense study drugs

- Obtain blood samples for laboratory assessments as follows:
  - Safety laboratory tests (serum chemistry, hematology, and coagulation)
  - Quantification of plasma HBV DNA levels
  - Qualitative HBsAg and HBeAg (HBsAb and HBeAb reflex testing will be performed as needed) (**Weeks 24 and 48 only**)
  - eGFRCKD-EPI
  - Blood sample for Fibrotest® (**Weeks 24 and 48 only**)
  - Blood sample for Vitamin D assessment (**Weeks 24 and 48 only**)
  - Blood sample for AFP (**Weeks 24 and 48 only**)
  - Blood sample for PK
  - 
  - Blood sample for PBMC (**Weeks 24 and 48 only**)
  - 
  - HBV resistance surveillance
- Dose in clinic and collect single blood sample for plasma PK between 15 minutes to 4 hours post-dose. Subjects who elect to dose in the evening the previous day are not required to have in-clinic dosing, the plasma PK samples from these subjects can be collected anytime (not timed) (**Weeks 8 and 24 only**)
- Urine pregnancy test (for all female subjects of child-bearing potential)
- Urinalysis (**Weeks 4, 12, 24, and 48 only**)
- Fasting blood sample for bone and renal biomarkers – no food or drinks, except water, at least 8 hours prior to blood collection (**Weeks 4, 12, 24, and 48 only**)
- Fasting urine sample for renal biomarkers (**Weeks 4, 12, 24, and 48 only**)
- Fasting blood sample for metabolic assessment (glucose and lipid panel [total cholesterol, HDL, direct LDL, and triglycerides]) – no food or drinks, except water, at least 8 hours prior to blood collection (**Weeks 24 and 48 only**)

[REDACTED]

[REDACTED]

[REDACTED]

[REDACTED]

[REDACTED]

[REDACTED]

[REDACTED]

[REDACTED]

[REDACTED]

[REDACTED]

[REDACTED]

[REDACTED]

[REDACTED]

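### Protocol Appendix 2 places in-clinic dosing at Weeks 4 and 8, but Section 6.3.1 places it, with the timed PK sample, at Weeks 8 and 24

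*Protocol*

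**What the plan says.** Section 6 of the protocol says that study procedures are tabulated in Appendix 2 and described in the text after it. It gives neither place precedence.

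- **Appendix 2, table.** The row "Dosing in-clinic" is marked under Week 4 and Week 8, and its Week 24 cell is empty. The plasma PK row is marked at Baseline and at Weeks 4, 8, 12, 20, 24, 36 and 48.
- **Appendix 2, footnote d** (attached to the dosing row). Subjects who dosed the evening before need not dose in clinic and "provide the single PK sample being collected at Week 4 and 8 visits".
- **Appendix 2, footnote m** (attached to the plasma PK row). "At Weeks 8 and 24 the plasma PK samples should be collected between 15 minutes and 4 hours post-dose".
- **Section 6.3.1.** "Dose in clinic and collect single blood sample for plasma PK between 15 minutes to 4 hours post-dose". The same bullet exempts previous-evening dosers and ends with its visit restriction: "the plasma PK samples from these subjects can be collected anytime (not timed) (Weeks 8 and 24 only".
- **Synopsis, Criteria for Evaluation.** "At Weeks 8 and 24 the PK sample should be collected between 15 minutes and 4 hours post-dose".
- **SAP Appendix 1** repeats the table, footnote d and footnote m.

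**The concern.** A post-dose sampling window means something only if the time of the dose is known, and dosing in clinic is the step that fixes it. The protocol gives two different pairs of visits for that step. A site following the table would arrange a dose in clinic at Week 4, where no post-dose window applies, and would see no prompt to arrange one at Week 24, where the window does apply.

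Week 24 is also a fasting visit for bone, renal and metabolic samples (Section 6.3.1), while TAF is to be taken with food (Section 5.3). When a subject doses on that morning relative to the blood draw is therefore not obvious unless the schedule says so.

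At stake is how the Week 24 concentrations can be interpreted. Section 8.7 lists and summarizes PK parameters for TAF and TFV descriptively and plots concentrations over time. If the Week 24 dose time rests on self-report, some samples meant to fall within 15 minutes to 4 hours after dosing may fall outside it or be impossible to place.

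**Working it through.** No arithmetic applies. The point concerns a visit schedule, and the plan has no calculation that depends on it (Section 8.9: "This is an exploratory study. No formal sample size calculation was performed"). The check is to read off the visits in each place and compare them.

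| Place | In-clinic dosing | Timed sample (15 min to 4 h post-dose) |
|---|---|---|
| Appendix 2, dosing row | Weeks 4, 8 | not stated |
| Appendix 2, footnote d | Weeks 4, 8 (with the single PK sample) | no window given |
| Appendix 2, footnote m | not stated | Weeks 8, 24 |
| Section 6.3.1 | Weeks 8, 24 | Weeks 8, 24 |
| Synopsis | not stated | Weeks 8, 24 |
| SAP Appendix 1 | as Appendix 2 | as Appendix 2 |

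1. **Between documents and sections.** In-clinic dosing is {4, 8} in Appendix 2 and {8, 24} in Section 6.3.1. The sets share Week 8 and differ at Weeks 4 and 24. The timed-sample visits are {8, 24} wherever they are stated.

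2. **Within Section 6.3.1.** Dosing and timed-sample visits agree, because one bullet states both.

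3. **Within Appendix 2.** They agree only at Week 8. Week 4 has in-clinic dosing and a PK draw but no window. Week 24 has a PK draw with a window but no in-clinic dosing mark.

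4. **Same procedure or two?** Footnote d concerns the single PK sample and exempts previous-evening dosers in nearly the same terms as Section 6.3.1. On their visible wording, the two appear to describe one procedure with different visits.

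5. **A related ambiguity.** Footnote d can be read as excusing evening dosers from giving the sample at all. Section 6.3.1 keeps their sample but leaves it untimed.

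**The case against.** Four points on the other side have force.

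**Section 6.3.1 does schedule the Week 24 dose.** A reader of Appendix 2 alone might infer that the protocol requires a timed Week 24 sample with no in-clinic dose behind it. That is true of the table only. The defect is a contradiction, not an omission. The Synopsis and footnote m do not help either side on dosing, since they state only the sampling window.

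**The table still tells the site to time the Week 24 sample.** Footnote m sits on the plasma PK row. A site using only the table knows the window and can ask when the dose was taken. Untimed samples are also already allowed for evening dosers, so the contradiction does not by itself create a mixture of timed and untimed data. This narrows the harm to loss of control over dose time, but does not remove it.

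**Redaction.** The 24-hour columns after Weeks 4 and 8 show only an adverse-event mark. Footnote k, a table row, Appendix 3 and parts of the PK text are blacked out. A hidden procedure may explain the Week 4 mark, so that mark cannot be called wrong. It would not explain the empty Week 24 cell against Section 6.3.1, nor footnote d's visible reference to the single PK sample.

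**Reach.** About one center is planned, about 25 subjects are assigned to TAF, and the visible PK analysis is descriptive. SAP Section 2.1.2 leaves PK out of the analyses repeated in the Final Analysis. It refers to a separate Week 24 SAP, which is not among the documents reviewed, so mistimed samples may already have been handled there.

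**Conclusion.** The contradiction is real and lies in operative text: Appendix 2 (row and footnote d, with the SAP copy) against Section 6.3.1. It changes what the site would do at two visits, Weeks 4 and 24, and leaves Week 8 consistent. The documents do not show which schedule was intended.

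The consequence is limited to the descriptive TAF and TFV concentration data. A reader might infer that half of the timed PK data are compromised, because one of the two timed visits is affected. The documents do not support that figure. It would require the site to have followed the table over Section 6.3.1 and every in-clinic doser's Week 24 sample to have missed the window despite footnote m. Nor does the coincidence with the primary time point matter: the Week 24 primary endpoints are change in eGFR and HBV DNA below 20 IU/mL, and neither depends on dose-to-sample time.

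The conclusion rests on reading footnote d and the Section 6.3.1 bullet as the same procedure. How many samples were actually mistimed cannot be determined from these documents.

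**What to change.** Reconcile the Appendix 2 dosing row, footnote d, footnote m, Section 6.3.1, the Synopsis and the copies in SAP Appendix 1, so that in-clinic dosing visits and timed-sample visits agree. If the Week 4 mark serves a separate procedure, give it its own row or footnote. State in footnote d whether evening dosers still give a sample. The choice of schedule is the sponsor's.

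The SAP reports the Week 24 and Week 48 analyses as already conducted, so correcting the table cannot change samples already taken. Wherever PK is reported, classify Week 8 and Week 24 samples by recorded dose-to-sample time. Flag those outside 15 minutes to 4 hours as untimed, and give the number in each class by visit. This assumes that dose and draw times were recorded; samples without them should be flagged as well.

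The cost is a correction to the table, footnotes and text, plus one derived variable in the PK summaries. No extra visits or samples are needed.
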